### 6.2.6 Analyses of the COMPASS MIND Substudy

Subclinical (i.e., covert) strokes are more frequent than clinically evident brain infarcts, with a prevalence of covert strokes of 15% to 20% in population-based cohorts with a mean age of 65 years.

The COMPASS MIND substudy is a magnetic resonance imaging (MRI) substudy evaluating the incidence of clinically silent brain infarcts and subclinical brain ischemia and the effect of the antithrombotic therapies being tested in COMPASS on covert cerebral ischemia, thereby providing additional information about mechanisms of disease and treatment benefits.

A total of 1,500 COMPASS participants will be invited to participate (500 subjects per treatment group, balanced for age, prior stroke, and hypertension). Participants will undergo limited brain MRI sequences at entry and near study end. Two-stage central interpretation blinded to treatment will be carried out, with all incident covert infarcts confirmed by a second independent interpreter. Subjects will have DNA collected at baseline and blood collected at baseline and at the 1 month visit.

Data related to the COMPASS MIND substudy will be reported separately.

#### 6.2.6.1 Variables of the COMPASS MIND Substudy

Outcomes of the COMPASS MIND substudy are:

- Covert brain infarcts  
(detected by blinded comparison of initial vs. end-study MRIs)

---

 Text modified as per modification 1 in integrated SAP, Version 4.1.

- Non-lacunar covert brain infarcts
- All incident strokes, including clinical strokes and all covert strokes

Furthermore, functional decline (based on SAGE), cognitive decline (based on MoCA and DSS), and biomarkers (C-reactive protein, NT-proBNP) will be assessed.

### 6.2.6.2 Statistical Analysis of the COMPASS MIND Substudy

The incidence of the COMPASS MIND substudy outcomes will be determined for each antithrombotic study treatment group. Two comparisons will be performed to compare

- rivaroxaban 2.5 mg bid + aspirin 100 mg od treatment with rivaroxaban placebo + aspirin 100 mg od (control), and
- rivaroxaban 5 mg bid + aspirin placebo treatment with rivaroxaban placebo + aspirin 100 mg od (control)

within the subpopulation included in the COMPASS MIND substudy.

Functional and cognitive decline as well as the predictive value of biomarkers as independent predictors of covert brain infarcts will be explored by means of descriptive statistics. Details of additional analyses will be described in a separate document; results will be reported separately.

### 6.2.7 Exploratory Analyses

In the unexpected event that the number of subjects who need to be declared as lost to follow-up is unexpectedly high and evidence suggests that the assumption of non-informative censoring cannot be adopted, additional sensitivity analyses might be performed in order to evaluate the robustness of the primary analysis. Where a subject is completely non-compliant with study follow up, the likelihood that this participant has experienced a study outcome will be derived and this information incorporated, as appropriate, in the analyses (Little et al., 2012 [13]). With SAP amendment v3.0, integrated in SAP, Version 4.0, sensitivity analyses to address the potential impact of missing data on the results of the primary analysis are described in Appendix 10.4.

The types of myocardial infarction and further details obtained on the myocardial infarction (MI) CRF Reports will be summarized at the event level by randomized antithrombotic study treatment group for subjects who experienced MI events during the study. The efficacy outcomes will also be evaluated by MI types according to the universal definition, see derivation document for details.

Symptoms, recovery status (Rankin scale), and further details obtained on the Stroke CRF Reports will be summarized at the event level by randomized antithrombotic treatment group for subjects who experienced 'stroke' events during the study.

Further characteristics related to heart failure obtained on the Heart Failure CRF Reports will be summarized at the event level by randomized antithrombotic treatment group for subjects who experienced 'heart failure' events during the study.

 Text added as per modification 4 in integrated SAP, Version 4.1.

 Text added as per modification 8 in integrated SAP, Version 3.0.

Further characteristics related to venous thromboembolisms obtained on the VTE CRF Reports will be summarized at the event level by randomized antithrombotic treatment group for subjects who experienced ‘venous thromboembolisms’ events during the study.

Further characteristics related to new diagnoses (/recurrence) of cancer obtained on the Cancer CRF Reports will be summarized at the event level by randomized antithrombotic treatment group for subjects who experienced ‘new diagnoses of cancer’ events during the study.

If applicable, information on subjects with multiple outcome events will be displayed as appropriate. Further tables summarizing study data will be specified in the TLF document.

Efficacy events occurring after the discontinuation of antithrombotic study treatment will be summarized for the subjects who have at least 1 day follow-up post last dose of antithrombotic study medication by treatment group and summarized by means of frequency tables. Specifically, events occurring within 30 days of permanent discontinuation of antithrombotic study medication will be the focus for the assessment of potential rebound effects.

Data collected with the International Physical Activity Questionnaire (IPAQ) and the Diet Questionnaire will be listed in the Appendix of the Clinical Study Report. Further analyses will be reported in a separate report.

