  - up until the Final Follow-up Visit date (inclusive), if the subject attends his/her Final Follow-up Visit or
  - up until the common trial close-out date, if the subject does not attend his/her Final Follow-up Visit.For subjects who die (a) after randomization but before the beginning of the common trial close-out window or (b) during the common trial close-out window but before their Final Follow-up Visit takes place, the date of the last follow-up contact is set to the death date. This date is only applicable to analyses for pantoprazole/placebo comparisons at the end of the study.
- Date of the last trial contact:  
The date of the last known documented contact with the subject or a third party (including data on subject survival status).
- Date of last double-blind dose of antithrombotic study treatment:  
The later date of
  - the last dose of rivaroxaban/rivaroxaban placebo study medication and
  - the last dose of aspirin / aspirin placebo study medication.For a subject with premature permanent discontinuation of any study medication, the corresponding last dose date(s) will be obtained from the Permanent Discontinuation CRF Report. If study medication was continued until the Final rivaroxaban/aspirin Follow-up Visit, the date of the last dose of the corresponding study treatment will be the date of the Final rivaroxaban/aspirin Follow-up Visit.  
If missing or incomplete, the date of last double-blind dose of antithrombotic study treatment is set to the latest logically possible date of antithrombotic study medication administration on or before the earliest of the subject's following dates, the date of the last contact for the rivaroxaban/aspirin comparison, the date of death, or the end of the rivaroxaban/aspirin arms close-out window, and no earlier than the randomization date.
- Date of last double-blind dose of pantoprazole study treatment:  
The date of the last dose of pantoprazole / pantoprazole placebo study medication of a subject randomized to pantoprazole.

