#### **Additional data scopes for secondary safety analyses for the rivaroxaban/aspirin randomization**

Additional secondary analyses of safety outcomes will be based on the safety analysis set (see Section 5.1.2). Subjects will be kept in the study group to which they were randomized. Additional data scopes will be defined to include all outcome events as follows:

- All outcome events for each subject occurring after the date and time of randomization and up until the global rivaroxaban/aspirin outcomes cut-off date (inclusive) (“ITT” data scope)
- All outcome events occurring after the date and time of randomization and up until 2 days following permanent discontinuation of double-blind antithrombotic study treatment documented in the database (“treatment emergent outcomes” data scope)
- All outcome events occurring after the date and time of randomization and up until 30 days following permanent discontinuation of double-blind antithrombotic study treatment documented in the database (“plus 30 days safety” data scope)
- All outcome events occurring after the date and time of randomization during the entire individual rivaroxaban/aspirin follow-up and wash-out periods documented in the database (“Rivaroxaban/aspirin Follow up + Wash out” data scope)

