### Sensitivity analyses

Sensitivity analyses will be performed to include all primary efficacy outcome events up until the minimum (earliest) of the Final rivaroxaban/aspirin Follow-up Visit date and the subject’s last contact date during the rivaroxaban/aspirin portion of the study.

In addition, the number of primary efficacy outcome events occurring after the Final rivaroxaban/aspirin Follow-up Visit until the rivaroxaban/aspirin Washout Telephone Visit, included in the clean database for the rivaroxaban/aspirin comparisons, will be summarized by rivaroxaban/aspirin study treatment group.

The plausibility of the proportional hazards assumption will be assessed by visually examining both the plot of the log of the negative log of Kaplan-Meier estimates of the survival function versus the log time for evidence of non-parallelism and the smoothed plot of the scaled Schoenfeld residuals to directly visualize the log hazard ratio (Grambsch and Therneau, 1994 [8]), for each stratum separately, and by including a time-treatment interaction term in the Cox model (time log transformed). The SAS code is adapted as follows:

 Text modified as per modification 1 in integrated SAP, Version 4.1.

```

PROC PHREG DATA = <dataset>;
  MODEL ttevalue * ttecnsr(0) = trtgrpnr trtltime / RL TIES=EFRON ALPHA=0.05;
  STRATA stratumn;
  trtltime = trtgrpnr*log(ttevalue);
RUN;

```

The significance of the interaction will be tested at the 5% type I error level. If the interaction is significant and there is strong evidence of non-proportionality from the plots, time-dependent hazard ratios will be estimated with the model that includes the interaction term.

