- if AE (/ SAE) occurred with causal relationship to study drug separately for each study medication, i.e., rivaroxaban/rivaroxaban placebo, aspirin/aspirin placebo, and pantoprazole/pantoprazole placebo,
- maximum intensity for any AE / any study-drug related AE,
- AE related deaths,
- discontinuation of study treatment use due to AE (as well as due to SAE).

A similar table showing overall summary information of AEs during run-in will be given.

In addition, frequency tables will summarize the number of subjects with

- any event occurring within 30 days before permanent study drug discontinuation
- any event occurring more than 2 days after permanent study drug discontinuation

for antithrombotic study medication.

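### The rebound table in SAP 6.2.7 starts the day after last dose and does not separate types of stop, so outcome events that triggered a stop can pull the rivaroxaban comparison toward no rebound

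*SAP*

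**What the plan says.** Section 6.2.7 defines the population and the event set together: "Efficacy events occurring after the discontinuation of antithrombotic study treatment will be summarized for the subjects who have at least 1 day follow-up" after the last dose. It gives the results as frequency tables by treatment group and then sets the purpose: "Specifically, events occurring within 30 days of permanent discontinuation of antithrombotic study medication will be the focus for the assessment of potential rebound effects". No lag, no rule for an event that led to the stop and no split by type of stop is stated.

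Elsewhere the SAP draws the line between on and off treatment two days later. The treatment-emergent scope in Section 4.5.2 runs "up until 2 days following permanent discontinuation of double-blind antithrombotic study treatment documented in the database", and Section 4.5.3 censors accordingly. In Section 6.4.2.1 the off-drug frequency table counts "any event occurring more than 2 days after permanent study drug discontinuation".

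For a subject who stops early, Section 4.5.1 says that "the corresponding last dose date(s) will be obtained from the Permanent Discontinuation CRF Report". A missing date "is set to the latest logically possible date of antithrombotic study medication administration on or before the earliest of the subject's following dates", among them the date of death.

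Section 6.2.1.2 also plans to summarize, by arm, "the number of primary efficacy outcome events occurring after the Final rivaroxaban/aspirin Follow-up Visit until the rivaroxaban/aspirin Washout Telephone Visit".

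**The concern.** Consider a subject who takes the last tablet on Monday and has a stroke on Tuesday, with the discontinuation form dated Monday. The stroke is the reason for the stop, yet it falls on day 1 of the rebound window. Under the safety scope the same day counts as on treatment.

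Such events arise roughly in proportion to each arm's on-treatment event rate. If rivaroxaban is effective, control supplies more of them, and the comparison is tilted toward no rebound in exactly the situation where rebound matters. Pooling adds to this. A stop at close-out is unrelated to the subject's health, whereas a premature stop often is related, so one table answers two different questions.

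At stake is a reassuring statement on a risk that the SAP itself names.

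**Working it through.** **1. The plan's own figures.** The rebound table has no stated figure. The only counts by arm are the planning counts in Section 4.4: 826 in control and 687 in each rivaroxaban arm. They reproduce: 826 + 687 = 1,513, and 826 + 2 × 687 = 2,200. The ratio is 687/826 = 0.83.

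**2. The windows side by side.**

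| Days after last dose | Treatment-emergent scope (4.5.2) | Off-drug AE table (6.4.2.1) | Rebound table (6.2.7) |
|---|---|---|---|
| 1-2 | counted, as on treatment | not counted | counted, as rebound |
| 3-30 | not counted | counted | counted, as rebound |

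Days 1-2 are thus on treatment for safety and off treatment for rebound.

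**3. Are close-out stops included?** The 30-day safety scope in Section 4.5.2 is also keyed to permanent discontinuation, and Section 4.5.3 notes that a subject who stops at the Final rivaroxaban/aspirin Follow-up Visit is covered by it. Where Section 4.2 means early stops, it adds the word premature; Section 6.2.7 does not. Against this, Section 3 uses permanent discontinuation for an early stop. Pooling is the natural reading but not a certain one, so both are computed.

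**4. Illustration with all stops pooled.** Inputs: 9,134 subjects per arm (Section 7); a control rate of 3.32% per year (Table 7-3), taken as the off-drug rate in every arm; and half of the planned events, because the arms were stopped after the first interim analysis: 826/2 = 413 and 687/2 = 343.5. Let f be the share of first primary events that end treatment and are dated at least one day after the last dose, inside the window. **f is an assumption.** R is the true rebound ratio.

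Background, days 3-30: 9,134 × 0.0332 × 28/365 = 23.3 per arm.

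Observed ratio = (343.5f + 23.3R) / (413f + 23.3)

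| f | Trigger events, control / rivaroxaban | R = 1.5 shows as | R = 1 shows as |
|---|---|---|---|
| 0 | 0 / 0 | 1.50 | 1.00 |
| 5% | 20.7 / 17.2 | 1.19 | 0.92 |
| 10% | 41.3 / 34.4 | 1.07 | 0.89 |
| 20% | 82.6 / 68.7 | 0.98 | 0.87 |

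The ratio reaches 1 for R = 1.5 when 69.5f = 0.5 × 23.3, that is, at f of about 17%.

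**5. Illustration with premature stops only.** Section 7 assumes discontinuation of 6%, 4.5% and then 3% per six months. Over 2 years (an assumed average): 9,134 × (1 − 0.94 × 0.955 × 0.97²) = 1,419 per arm. Background over 30 days at 3.3% per year: 1,419 × 0.033 × 30/365.25 = 3.8 events. With the same 413 and 343.5 events, R = 1.5 shows as 1.15, 1.04 or 0.94 at f = 1%, 2% or 5%, and is cancelled at f of about 2.8%.

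**The case against.** A reader might infer that the MI, stroke or death that ended treatment is in general counted as rebound. The documents do not support that. Only events after discontinuation count, in subjects with at least one day of follow-up after last dose. A trigger event dated on or before the last dose stays out. Table 10-2 foresees a last dose on the day of death, and the rule for missing last-dose dates pushes fatal triggers out of the window rather than in. The SAP also does not say that an outcome event requires stopping; Section 3 encourages subjects to stay on treatment. All of this stands and limits f.

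Further points stand in part:

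- f is nowhere in the documents. It is applied above to all first events, although some occur long after treatment has ended.
- The control excess holds only under the planning alternative.
- With all stops pooled, cancelling a doubling takes f of about 36%: 30-day background 9,134 × 0.033 × 30/365.25 = 24.8, divided by 69.5. Attenuation, however, begins far below that.
- The table is exploratory and descriptive, and further tables are left to a TLF document that is not shown.
- The 2-day limits belong to safety scopes, and a different window for rebound is not in itself an error. Dropping days 1-2 could also remove a true early rebound.

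The strongest objection is that Section 6.2.1.2 already counts washout events by arm. It does not repair the point: it covers primary events between the final visit and the washout call in all subjects, including those who had stopped long before, so it does not isolate the effect of stopping. The off-drug table in Section 6.4.2.1 belongs to adverse-event reporting, from which study outcomes are largely exempt.

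**Conclusion.** The point holds in limited form. The rebound window overlaps the SAP's own on-treatment window, and the text does not separate event-triggered stops from stops at close-out. If rivaroxaban works as planned, the resulting bias runs toward no rebound.

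Its size cannot be fixed from the documents. At assumed f of 5% to 20%, a 1.5-fold rebound shrinks to between 1.19 and 0.98 with all stops pooled, and an f of a few percent is enough to hide it if only premature stops are tabulated. These figures assume a common off-drug event rate, the planned 687-to-826 ratio and f equal across arms. They illustrate direction and sensitivity and are not a forecast. Since no test or decision rule depends on the table, this is a worthwhile clarification and leaves the primary analysis untouched.

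**What to change.** Reword the rebound paragraph of Section 6.2.7 to give two tables by arm, each with denominators and 95% CIs:

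- (a) main: subjects still on treatment who stopped at the Final rivaroxaban/aspirin Follow-up Visit, followed to the washout call;
- (b) supportive: subjects who stopped prematurely, followed for 30 days after last dose.

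In each, show days 1-2 separately from days 3-30 rather than dropping them, and flag events recorded as the reason for stopping. The reason for discontinuation, the last-dose date and the washout contact are already collected.

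The cost is one paragraph and one extra re-cut descriptive table, with smaller counts per cell. As a rough guide for table (a), 9,134 − 1,419 = 7,715 subjects per arm give 7,715 × 0.0332 × 28/365 = about 20 background events over days 3-30, before allowing for deaths and losses. The confidence intervals are therefore needed to show how little a ratio near 1 would exclude.

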### **6.3 Pharmacokinetics/pharmacodynamics**

Not applicable.

### **6.4 Safety**

#### **6.4.1 Primary Safety**

##### **6.4.1.1 Primary Safety Variable**

The primary safety variable is the time (in days) from randomization to the first occurrence of the following primary safety outcome:

modified International Society on Thrombosis and Haemostasis (ISTH) major bleeding, defined as:

- fatal bleeding, and/or  
symptomatic bleeding in a critical area or organ, such as intracranial, intraspinal, intraocular, respiratory, liver, pancreas, adrenal gland or kidney, retroperitoneal, intraarticular or pericardial, or intramuscular with compartment syndrome, or bleeding into the surgical site requiring reoperation, and/or
- bleeding leading to hospitalization

The primary safety time-to-event variable will be derived in a manner similar to that described in Section 6.2.1.1 for the primary efficacy variable.

In addition to the analysis and censoring scheme according to the intention-to-treat principle, secondary safety analyses will be performed using time-to-event variables with censoring according to the censoring schemes for secondary safety analyses as described in Section 4.5.3.

### 6.4.1.2 Primary Safety Analysis

The principal analysis of the primary safety outcome will be based on the intention-to-treat principle. The analysis will follow similar methodology as the analysis of the primary efficacy outcome described in Section 6.2.1.2.

In addition, the primary safety outcome will be analyzed based on the safety analysis set and the secondary safety data scopes and corresponding censoring rules defined in Sections 4.5.2 and 4.5.3.

The number of subjects with multiple primary safety outcomes will be summarized, and further analyzed if applicable. Further details characterizing the bleeding events collected on the Bleeding CRF Report will be summarized by means of descriptive statistics and frequency tables.

### 6.4.1.3 Safety Subgroup Analyses

Subgroup analyses for the primary safety outcomes will be performed based on ITT analysis set and scope and based on the safety analysis set and treatment-emergent data scope similar to the methodology outlined in Section 6.2.5.

### 6.4.2 Other Safety Analyses

For the purposes of this trial, the following events will be captured on the CRF as study outcome events and will be reported as primary, secondary, or tertiary outcomes or as outcome of the pantoprazole randomization (see Section 6.2):

cardiovascular death, myocardial infarction, stroke, major bleeding, cardiovascular hospitalization, venous thromboembolism, revascularization, amputation, angina, heart failure, resuscitated cardiac arrest, new diagnosis (/recurrence) of cancer, gastrointestinal bleeding, ulcer, perforation, or obstruction, and other expected non-cardiovascular causes of hospitalization and death.

#### 6.4.2.1 Adverse Events

A Serious Adverse Event / Event of Special Interest (SAE/ESI) CRF Report is to be completed when a subject has an event that is (a) not an exempted study outcome and serious, or (b) an event of special interest. In addition, any AEs of particular concern to the investigator may be recorded on the CRF. While AEs that are not serious but that lead to permanent discontinuation of study medication will be captured in the CRF, non-serious AEs that do not lead to discontinuation of study medication will not be collected.

Additional hospitalization data will be collected on the CRF to permit the analysis of MRU data, which will be reported separately in another stand-alone report.

Analyses of reported adverse events will be performed based on

- the ITT analysis set using the “ITT” data scope
- the safety analysis set and the “treatment emergent outcomes” data scope

as outlined in Section 4.5.2.

---

 Text modified as per modification 4 in integrated SAP, Version 4.1.

In case of uncertainty (e.g., missing or incomplete dates), adverse events will be classified as “treatment emergent” and be included in the ITT scope following the worst case approach. In addition, those AEs occurring during the run-in phase and those AEs occurring after discontinuation of anti-thrombotic study treatment will be summarized, respectively.

The original terms used by investigators to report AEs via the CRFs will be coded using the Medical Dictionary for Regulatory Activities (MedDRA). All reported serious adverse events, adverse events leading to discontinuation of study drug, and adverse events of special interest with onset at the date of or after randomization will be summarized by means of AE tables.

For each AE and serious adverse event (SAE), the number and percentage of subjects who experienced at least 1 occurrence of the given event will be tabulated according to the affected primary system organ class (SOC) and preferred term (PT) by randomized antithrombotic study treatment group. A total column will be included in all safety summaries. After study close-out for the pantoprazole/placebo portion of the study, similar tables will display the same information by PPI study treatment group, see also analyses described in Section 5.

Frequency tables, showing an overall summary of number of subjects with AEs and SAEs, will be given, and will include the following information.

- if AE (/ SAE) occurred with causal relationship to study drug separately for each study medication, i.e., rivaroxaban/rivaroxaban placebo, aspirin/aspirin placebo, and pantoprazole/pantoprazole placebo,
- maximum intensity for any AE / any study-drug related AE,
- AE related deaths,
- discontinuation of study treatment use due to AE (as well as due to SAE).

A similar table showing overall summary information of AEs during run-in will be given.

In addition, frequency tables will summarize the number of subjects with

- any event occurring within 30 days before permanent study drug discontinuation
- any event occurring more than 2 days after permanent study drug discontinuation

for antithrombotic study medication.

